## 2 SAMPLE SIZE AND STATISTICAL POWER CONSIDERATION

The hypothesis for the primary effectiveness endpoint will be tested using Finkelstein-Schoenfeld test (Finkelstein et al 1999). With the assumed effect sizes and variability for Scenario 1 outlined in Table 1 (Section 11.1 of the CIP), 57 subjects per arm will provide >99% power for the primary effectiveness endpoint based on Finkelstein-Schoenfeld test statistics at the two-sided significant level alpha ( $\alpha$ ) of 0.05. Taking into consideration higher than anticipated variability observed with the 24hr CTD variable, in scenario 2 we consider the same effect sizes in the 3 components and a larger variability (double of that in Scenario 1). In that instance the needed sample size is 65 per arm to achieve 92% power.

With this same sample size per arm, power for the key secondary endpoint is estimated >99.9%, and for 24-hour chest tube drainage (mL), >99.9%, based on a two-sample t-test assuming equal variance and a two-sided alpha of 0.05. Assuming unequal variances, power for comparisons of platelet transfusions (volume [mL]) and PRBC transfusions (volume [mL]), is estimated at 98.0% and 96.7%, respectively.

Allowing for ~7% dropouts, approximately 140 subjects will be randomized in a 1:1 ratio to the treatment and control arms to ensure that 130 subjects (65 per arm) will be evaluable for the primary effectiveness analysis.

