Additional powered secondary endpoints include 24-hour CTD (volume [mL]), total platelet transfusions (volume [mL] and units), and total PRBC transfusions (volume [mL] and units) during the index hospitalization. Twenty-four-hour CTD (mL) will be assessed via two-sample t-test for mean difference. The transfusion endpoints will all be analyzed using two-sample t-tests for mean differences, and Fisher-Freeman-Halton exact tests for units. In the event the assumptions for a two-sample t-test are not met in any of the above, a nonparametric test such as a Mann-Whitney test will be employed, with median and range values provided in the output. Other secondary endpoints include the remaining Win Ratio component parts: proportions of fatal perioperative bleeding events will be assessed via Fisher's exact test; and proportions of UDPB events (by category) will be assessed via a Fisher-Freeman-Halton exact test. The secondary endpoint of surgical re-exploration for bleeding will take into account time to re-exploration.

Sample Size

Up to 140 subjects will be randomized in a 1:1 ratio to the treatment and control arms. Sample size is based on assumed response rates for the primary effectiveness Win Ratio sub-components, and can be calculated via an iterative simulation process with programming code available in an appendix to Redfors et al. (2019).[11] With a Finkelstein-Schoenfeld test, total of 57 subjects per arm ensures power of $\geq 99.7\%$, using a two-sided alpha (α) of 0.05. With this same per arm sample size, power for the key secondary endpoint is estimated at $>99.9\%$, and for 24-hour chest tube drainage (mL), $>99.9\%$, based on a two-sample t-test assuming equal variance and a two-sided alpha of 0.05. Similarly, although assuming unequal variances, power for comparisons of platelet transfusions (volume [mL]) and PRBC transfusions (volume [mL]), is estimated at 98.0% and 96.7%, respectively.

Analysis Populations

Enrolled subjects include all subjects who provide informed assent/consent. Enrolled subjects who do not meet criteria for study eligibility are screening failures and will exit the study.

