11.1. Statistical Power and Sample Size Determination

Up to 140 subjects meeting the study inclusion criteria (**Section 4.4.1**) will be randomized in a 1:1 ratio to the treatment and control arms. As noted above (**Section 6.2**), in order to maintain the balance between sites in terms of numbers of subjects randomized, study sites will be capped at randomizing a maximum of 15% of the overall study sample. Allowing for 5% dropouts, at total of 114 subjects (57 per arm) are expected to be evaluable for effectiveness and safety. Sample size is based on assumed effect size for the primary effectiveness Win Ratio sub-components (**Table 3**), and can be calculated via an iterative simulation process with programming code available in an appendix to Redfors et al. (2019).[11] With a Finkelstein – Schoenfeld test, a total of 57 subjects per arm ensures power of $\geq 99.7\%$ for the primary effectiveness endpoint at the final analysis, using a two-sided alpha (α) of 0.05. [10] With this same per arm sample size, power for the key secondary endpoint is estimated at $>99.9\%$ assuming a $40\% \pm 40\%$ mean difference between treatment and control, based on a two-

sample t-test assuming equal variance and a two-sided alpha of 0.05. For the 24-hour CTD secondary endpoint, assuming a treatment arm volume of 480 ± 253 mL and control arm volume of 800 ± 253 mL [8] [a discount is applied (see **Table 3** for details) to bring the Active arm up to ~40% reduction on the Control arm], power is similarly estimated at >99.9%. Power for comparisons of platelet transfusions between the treatment arm (0.32 ± 0.9 units) and control arm (1.6 ± 2.2 units) [13] is estimated at 98.0%, based on a two-sample t-test assuming unequal variance and a two-sided alpha of 0.05. Similarly, power for PRBC transfusions between the treatment arm (1.3 ± 2.1 units) and control arm (4.4 ± 5.7) [13] is estimated at 96.7%.

Overall study sample size is designed to provide adequate power for the primary effectiveness endpoint, the key secondary endpoint, and succeeding three secondary endpoints. Sample size and power for all secondary endpoints were calculated using PASS 2021 (NCSS, LLC. Kaysville, UT, USA, ncss.com/software/pass).

The null hypothesis for the primary composite endpoint is represented by:

H_0 : The distributions of the components are the same in the two treatment groups.

The alternative hypothesis for the primary composite endpoint is represented by:

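### SAP Section 2 attaches secondary-endpoint powers from 57 per arm and SD 253 to the 65-per-arm design; at its own SD of 500 mL, 24-hour CTD power is about 95%, not above 99.9%

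*SAP*

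**What the plan says.** SAP Section 2 and its Table 1 give two scenarios with the same effects. Fatal bleeding is 3.0% in both arms, UDPB class 2 or higher is 24.3% against 40.5%, and mean 24-hour CTD is 480 against 800 mL. Scenario 1 uses SD 253 and 57 per arm (99.7% primary power). Scenario 2 uses SD 500, which the text introduces as a response to variability seen in the CTD data: "In that instance the needed sample size is 65 per arm to achieve 92% power".

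The paragraph that follows begins "With this same sample size per arm, power for the key secondary endpoint is estimated >99.9" percent. It continues with CTD power, "for 24-hour chest tube drainage (mL), >99.9%, based on a two-sample t-test assuming equal variance and a two-sided alpha of 0.05", and then "power for comparisons of platelet transfusions (volume [mL]) and PRBC transfusions (volume [mL]), is estimated at 98.0% and 96.7%, respectively". No SD is attached to any of these. The section closes by sizing the trial: "Allowing for ~7% dropouts, approximately 140 subjects will be randomized in a 1:1 ratio to the treatment and control arms", to leave 130 evaluable (65 per arm).

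The same powers appear in the protocol for 57 per arm. Protocol 11.1 gives the inputs: CTD SD 253 mL, and transfusions in units, for example "Power for comparisons of platelet transfusions between the treatment arm (0.32 ± 0.9 units) and control arm (1.6 ± 2.2 units". The protocol synopsis nevertheless labels the transfusion comparisons as volume: "Similarly, although assuming unequal variances, power for comparisons of platelet transfusions (volume [mL]) and PRBC transfusions (volume [mL". SAP 5.4.1.2 makes volume the main transfusion analysis and units supplemental.

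Protocol 11.1 also randomises up to 140 and says "Allowing for 5% dropouts, at total of 114 subjects (57 per arm) are expected to be evaluable for effectiveness and safety".

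**The concern.** The SAP raised the CTD standard deviation when it recalculated the primary composite, in which CTD is only the third component. It left the power of CTD as an endpoint in its own right at the old value. The nearest antecedent of the opening words of the paragraph is 65 per arm, and that is the size the section goes on to justify, so the printed figures read as properties of the updated design.

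CTD is third in the fixed testing sequence (SAP 3.7 and 5.1), ahead of platelet and PRBC transfusions. A non-significant CTD result makes both of those p-values nominal. Protocol 11.1 says the sample size is meant to provide adequate power for these endpoints, so a reader judging the sequence needs the CTD power under the variability the SAP itself adopted.

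Two smaller faults sit beside it. The transfusion powers carry a unit for which neither document gives inputs, and the protocol's evaluable count agrees neither with its own dropout rate nor with the SAP.

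**Working it through.** **Method.** All powers are two-sided at 0.05. For equal variances, SE = SD × √(2/n), the noncentrality is δ/SE, and power comes from the noncentral t with 2n − 2 degrees of freedom. For the transfusions, SE = √((s₁² + s₂²)/n) with Satterthwaite degrees of freedom.

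**Reproducing the printed figures at 57 per arm with the Protocol 11.1 inputs**

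| Endpoint | Inputs | SE | δ/SE | Power | Printed |
|---|---|---|---|---|---|
| Key secondary | 40 points, SD 40 | 7.49 | 5.34 | 99.96% | >99.9% |
| 24-hour CTD | 320 mL, SD 253 | 47.4 | 6.75 | >99.99% | >99.9% |
| Platelets (units) | 0.32 (0.9) vs 1.6 (2.2), δ = 1.28 | 0.315 | 4.07 | 98.0% | 98.0% |
| PRBC (units) | 1.3 (2.1) vs 4.4 (5.7), δ = 3.1 | 0.805 | 3.85 | 96.7% | 96.7% |

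All four match, so this is where the printed figures come from.

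**The same calculations at 65 per arm**

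| Endpoint | SD | SE | δ/SE | Power |
|---|---|---|---|---|
| Key secondary | 40 | 7.02 | 5.70 | 99.99% |
| 24-hour CTD | 500 | 500 × √(2/65) = 87.7 | 320/87.7 = 3.65 | **95.2%** |
| 24-hour CTD | 506 (exactly twice 253) | 88.8 | 3.61 | 94.7% |
| 24-hour CTD | 253 | 44.4 | 7.21 | >99.99% |
| Platelets (units) | 0.9 / 2.2 | 0.295 | 4.34 | 99.0% |
| PRBC (units) | 2.1 / 5.7 | 0.753 | 4.11 | 98.2% |

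At 57 per arm and SD 500, CTD power is 92.3%. Power of 99.9% at 65 per arm needs an SD of about 358 mL or less; at SD 500 it needs about 126 per arm.

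**Effect of the planned ANCOVA.** SAP 5.4.1.1 analyses CTD with treatment and, when deemed appropriate, type of surgery. The documents do not say how much CTD variance surgery type explains, so I assume R² from 0 to 0.20. With residual SD = 500 × √(1 − R²) and 127 degrees of freedom, power is 95.2% (R² = 0), 96.0% (0.05), 96.8% (0.10) and 98.2% (0.20). Reaching 99.9% needs R² of about 0.49.

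**Primary endpoint.** Simulating the Finkelstein-Schoenfeld test (4,000 runs, normal CTD, independent components) gives 99.7% at 57 per arm with SD 253 and about 92% at 65 per arm with SD 500. Both agree with SAP Table 1.

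**Dropout arithmetic**

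- Protocol 11.1: 140 × (1 − 0.05) = 133, not 114.
- The printed 114 is 120 × 0.95.
- Going from 140 to 114 is a loss of 1 − 114/140 = 18.6%.
- SAP: 140 × 0.93 = 130.2, which agrees with 130.

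**The case against.** The sentence can be read another way. Its opening closely follows the protocol wording, where it refers to 57 per arm and SD 253, and SAP Section 2 cites Protocol 11.1. On that reading every printed power is right. This deserves weight, but such figures describe neither the size the section then justifies nor the CTD variability it says was observed. No reading gives above 99.9% at SD 500.

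The 95% is itself indicative. A normal distribution with mean 480 and SD 500 puts about 17% of the treatment arm below zero, and the SAP uses gamma regression for CTD in Section 3.5. With gamma-distributed CTD and the same means and SDs, simulation gives about 94% for the t-test and about 99.6% for the Mann-Whitney test, which is the protocol's fallback. The gap therefore depends on the distribution and the test, but neither result restores the printed figure.

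The transfusion part matters least. The printed values are conservative at 65 per arm, and power would be the same in mL and in units if volume per unit were roughly constant. The documents give no conversion, so the label still needs support.

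Protocol 11.1 says up to 140, so 114 could be meant as the number needed rather than the number expected. The sentence itself presents it as the expected evaluable count after 5% dropout. It looks like text left from before enrolment was increased.

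Finally, about 95% is ample for a secondary endpoint. That is right, and it limits the point to what the plan states about its power.

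**Conclusion.** The concern holds.

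- **CTD:** stated power is above 99.9%; at the SAP's own SD of 500 and 65 per arm it is 95.2% for an unadjusted t-test, about 5 points lower. The chance of the sequence stopping at that step, if reached, is about 4.8% instead of under 0.1%. This rests on the planned 320 mL difference and normal data. ANCOVA gives 95.2% to 98.2% over the assumed R² of 0 to 0.20.
- **Transfusions:** the printed powers belong to 57 per arm and to units. They are 1.0 and 1.5 points too low for 65 per arm, and no mL inputs support the label.
- **Evaluable count:** Protocol 11.1 is off by 19 (114 against 133) if all 140 are randomised.

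The key-secondary power, the two primary powers and the SAP's 140 / about 7% / 130 are sound. The trial is not undersized, and no test, alpha, population or enrolment target is affected. The correction should be made because these are the sample-size statements of a pivotal trial and, as written, do not show which n and SD they use.

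**What to change.** **SAP Section 2.** State CTD power as about 95% at 65 per arm and SD 500, and above 99.9% at SD 253. Note that this is for an unadjusted t-test, whereas SAP 5.4.1.1 plans ANCOVA. Label the transfusion powers as based on units and give their n (98.0% and 96.7% at 57 per arm; 99.0% and 98.2% at 65), or recompute them from stated mL means and SDs.

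**Protocol.** In 11.1, replace the 5% / 114 sentence with figures that agree with the SAP: about 7% dropout and 130 evaluable, 65 per arm. In Table 3 and the synopsis, which cite only 57 per arm, add the SAP's Scenario 2 (SD 500, 65 per arm, 92.1%) beside the original one. Correct the mL label in the synopsis in the same way as in the SAP.

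**Cost.** A less favourable stated CTD power, a SAP text revision and a minor protocol amendment, with at least IRB notification under Protocol Section 16. Enrolment and analyses do not change.

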**Table 1. Effect Size Assumptions with Power and Sample Size Estimates**

Scenario	Sample size Per Group	Effect Size						Power	
		Component #1		Component #2		Component #3			
		Fatal Bleeding		UDPB (Class ≥2)		24hr CTD			
Treatment Event	Control Event	Treatment Event	Control Event	Treatment Mean (SD)	Control Mean (SD)				
1	N= 57	3.0%	3.0%	24.3%	40.5%	480 (253)	800 (253)	99.7%	
2	N=65	3.0%	3.0%	24.3%	40.5%	480 (500)	800 (500)	92.1%	

### 3 GENERAL ANALYSIS DEFINITIONS

#### 3.1 Visit Windows

Nominal visit days/time will be used in the analysis, unless specified otherwise. Refer to the Table 6, Schedule of Assessments in the study protocol for details on study periods.

#### 3.2 Analysis Sets

##### 3.2.1 Modified Intent-to-Treat Population

The modified intent-to-treat (mITT) population will consist of all randomized subjects who undergo the index surgical procedure and receive a study device (whether DrugSorb™-ATR or sham). This is the primary population for all the effectiveness analyses.

##### 3.2.2 Intent-to-Treat Population

The intent-to-treat (ITT) population will consist of all subjects who have been randomized to the study. This population will be used for supplementary effectiveness analyses.

##### 3.2.3 Per Protocol Population

The Per Protocol (PP) Population will include all mITT subjects who have no major protocol deviations. This population will be used for supplementary effectiveness analyses.

##### 3.2.4 Population of Special Interest

The isolated-CABG (i-CABG) populations will consist of mITT or PP subjects who undergo i-CABG as the index surgical procedure. The subjects who undergo all other types of surgery including valve replacement, valve repair, aortic, structural or combination of CABG plus another major procedure will be excluded. Those two populations (i-CABG mITT and i-CABG PP populations) will be used for supplementary effectiveness analyses.

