6.1. Pre-randomization Stratification

Pre-randomization stratification will be performed on two levels, based on the rationale described below:

1. By study site in order to control for differences in institutional protocols that could impact outcomes. These may include but are not limited to different institutional practices for drug and transfusion administration intra-op and post-op. Institutions may also differ in metrics utilized for clinical decision-making (e.g., delaying sternal closure, or surgical reoperation).
2. By the intended surgical procedure in order to control for differing procedure-specific

bleeding risks, and duration of CPB (i.e., device exposure) as detailed below:

- CABG alone (irrespective of number of grafts); or
- All other cardiothoracic procedures (including but not limited to combination procedures (i.e., CABG + aortic/mitral valve procedures, double heart valve procedures, etc.), aortic intervention, and combination aortic + cardiac interventions).

Of note, during the pre-procedure and intraoperative periods, the intended procedure may change due to factors that could not be adequately determined or anticipated in advance of the procedures. These day-of-surgery changes to the planned operations may result in the completion of a procedure that a) does not align with eligibility criteria, or b) alters stratification. Any change to the intended procedure occurring on the day of surgery that is not updated in the final IxRS assignment will be considered a protocol deviation. These protocol deviations will be noted in a deviation log for data analysis considerations at the conclusion of the trial. Subjects who have changes to their intended procedures on the day of surgery should progress through the study as in the protocol.

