11.4. Subgroup Analysis

The primary effectiveness endpoint will also be analyzed across the clinically meaningful subgroups, including but not limited to those outlined below:

- Planned surgery type (CABG alone vs. all other types of surgery)
- Key demographic factors including age (<65 vs. ≥ 65 years old) and sex (M/F)
- EuroScore II score
- STS Risk score (low, intermediate, high)
- NYHA heart failure class (1, 2, 3, 4)
- Left ventricular ejection fraction [according to the ACC classification: $\geq 50\%$ (normal), 40-49% (mild dysfunction), 30-39% (moderate dysfunction), <30% (severe dysfunction)]
- Baseline thrombocytopenia (platelet count $< 150,000 \mu/L$, $\geq 150,000 \mu/L$)
- Prior MI (Y/N)
- Prior stroke (Y/N)
- Prior hypertension (Y/N)
- Prior hyperlipidemia (Y/N)
- Diabetes mellitus (Y/N)
- Chronic obstructive pulmonary disease/COPD (Y/N)
- Current or prior tobacco use (Y/N)
- Prior sternotomy (Y/N)
- Drug removal

Additional details on subgroup analyses will be provided in the SAP.

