Vital signs ^h	X				SOC	X	X	SOC	SOC	SOC ^s	SOC
CPB duration ⁱ			X								
DrugSorb TM flow rate & flow duration ⁱ			X								
Surgical procedure type ^j			X								
Activated Clotting Time (ACT) ^k			X	X							

Study Procedures	Screening	Pre-CPB	Operation	Post-CPB	Post-Operation					Follow-up Visit/End of Study/Early Termination
	Up to 2 days prior to the day of Operation	Within 2 hours before start of operation (i.e., skin incision)	From chest incision to chest closure	Within 30 min after end of CPB	ICU Admission	POD 1	POD 2	POD 3	POD 4	
Timepoint										
Arterial Blood Gas (ABG) ¹			X	X	X					
Blood products ^m	X				X	X	X	X	X ^s	
Operation blood loss and drainage ^m			X							
Post-Operation chest tube drainage					X-----X					
Post-Op blood loss & bleeding ^m					X	X	X	X	X ^s	X
Daily assessment						X	X	X	X	X ^s
Adverse events ⁿ	X	X	X	X	X	X	X	X	X	X
Ventilation and mechanical support ^o					X	X	X	SOC	SOC	SOC
FiO2 ^p					X	X	X	SOC	SOC	SOC
Vasopressor requirements ^q					X	X	X	SOC	SOC	SOC

Abbreviations: AE = adverse event; CPB = cardiopulmonary bypass; D = day; h = hour; eCRF = electronic case report form; ICF = Informed Consent Form; ICU = Intensive Care Unit; POD = post-operative day; SOC = standard of care.

^a Authorization or informed consent must be obtained at Screening (see Appendix 3)

^b Body mass index will be calculated from the subject's height and weight measurements obtained at Screening or from the values in the medical record in the current hospital admission.

^c Pre-randomization stratification will be performed based on the *planned* surgical procedure, which may differ from the performed procedure.

^d Blood samples will be collected for the determination of plasma ticagrelor concentration at a designated bioanalytical laboratory using a validated assay. The pre-CPB blood sample will be drawn prior to the start of cardiopulmonary bypass and can be up to 2hrs prior to skin incision. The post-CPB blood sample will be drawn as soon as possible following the end of CPB, and no later than 30min after the subject has been disconnected from the CPB circuit. During the procedure, while the subject is on CPB, serial sampling will be obtained q30±15min up through 2hrs of CPB. If the procedure requires a CPB time of <2hrs, then sampling will be q30±15min only up through completion of the CPB.

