##### 3.2.5 Safety Analysis Population

The safety analysis (SA) population will include all enrolled subjects who are treated with a study device. Similarly, for the population of special interest, i-CABG SA population will consist of SA population who are treated with a study device and undergo an i-CABG procedure.

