#### 3.3 Randomization/Blinding

All subjects will be randomized in a one to one (1:1) ratio to either the control arm (SoC) or the treatment arm (SoC + DrugSorb™-ATR device). Pre-randomization stratification will be performed by study site, and by type of intended surgical procedure - either:

- CABG alone (irrespective of number of grafts); or
- All other cardiothoracic procedures (including but not limited to combination procedures [i.e., CABG + aortic/mitral valve procedures, double heart valve procedures, etc.], aortic interventions, and combination aortic + cardiac interventions).

Of note, patients undergoing undergo CABG + minor add-on procedures (e.g., left atrial appendage clipping, IABP or Impella placement, etc.) that do not (in the opinion of the investigator) significantly increase operative complexity or bleeding risk are included in the CABG alone category for Type of planned cardiothoracic surgery. Please see Section 6.1 of the CIP for additional details of pre-randomization stratification. Randomization is implemented via an Interactive Voice/Web response (IxRS) system.

Neither the subjects nor the site personnel have the treatment assignment information during the study period, unless specified in **Section 6.3** of the CIP. The blinded study team is blocked from every subject's treatment assignment before the data base lock for unblinding. Please see **Section 6.3** of the CIP for additional details of study blinding.

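### The i-CABG sets follow the operation performed, not the planned-surgery stratum used at randomisation, so they are neither the randomised CABG-alone stratum nor the protocol's planned-surgery subgroup

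*SAP*

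**What the plan says.** **Membership.** SAP 3.2.4 states that the i-CABG populations "will consist of mITT or PP subjects who undergo i-CABG as the index surgical procedure". Subjects with valve, aortic or structural surgery are left out, and a "combination of CABG plus another major procedure will be excluded". SAP 3.2.5 carries the rule into safety: the "i-CABG SA population will consist of SA population who are treated with a study device and undergo an i-CABG procedure".

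**Randomisation.** SAP 3.3 says "Pre-randomization stratification will be performed by study site, and by type of intended surgical procedure". Protocol 6.1 and 9.1.1 agree.

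**Planned and performed surgery can differ.** Note c to Table 6 (protocol Appendix 4) says stratification uses the planned procedure, "which may differ from the performed procedure". Protocol 6.1 says that "during the pre-procedure and intraoperative periods, the intended procedure may change due to factors that could not be adequately determined or anticipated in advance". It then makes a protocol deviation of "Any change to the intended procedure occurring on the day of surgery that is not updated in the final IxRS assignment".

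**Subgroup.** Protocol 11.4 lists "Planned surgery type (CABG alone vs. all other types of surgery" as a subgroup factor. SAP 3.6 lists CABG against other procedures without saying whether planned or performed surgery is meant.

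**Use of the sets.** The i-CABG mITT and PP sets carry the primary analysis (SAP 5.2.4.3), the supplementary composite (5.2.5), the key and additional secondary endpoints (5.3, 5.4), the exploratory endpoints (5.5) and the PK analyses (Appendix A). The i-CABG SA set carries safety (6.1). SAP 3.7 applies the same testing order to i-CABG as to the main analysis. SAP 3.2.4 labels the effectiveness analyses supplementary.

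**The concern.** A subgroup fixed before randomisation keeps the randomised comparison within it. Here that subgroup is the planned CABG-alone stratum. A subgroup defined by what happened in theatre has no such guarantee. Its arms are comparable only if the events that decide membership are unrelated to arm.

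The performed operation is such an event. Protocol 3 says surgery other than CABG alone has a significantly different profile of bleeding risk and CPB duration, so subjects who cross the line in either direction are likely to be prognostically different from those who stay.

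Two things are at stake. First, the SAP's i-CABG result and the protocol's planned-surgery subgroup are about different sets of subjects, and nothing in either document connects them. Second, i-CABG has its own copy of the testing hierarchy, so its result will be read as more than one line in a subgroup table. A reader of that result will ask whether the set was fixed in advance, and as written it was not.

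**Working it through.** No figure in the documents bears on this point. They give no i-CABG sample size and no rate of change from planned to performed surgery. The check is therefore a comparison of sections, followed by a sizing exercise on assumed inputs.

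**1. Order of events**

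| Step | When | Source |
|---|---|---|
| Planned surgery type entered, subject randomised | Before surgery starts | Protocol 6.1, 6.2 |
| Device flow starts | Start of CPB | Protocol 2.5 |
| Intended procedure may change | Before or during the operation | Protocol 6.1 |
| Performed operation final | End of operation | Follows from the above |
| i-CABG membership | Uses the performed operation | SAP 3.2.4, 3.2.5 |

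Membership is therefore final only after randomisation. For a change made during CPB it is also after device start. No section ties i-CABG to the IxRS stratum or specifies an i-CABG analysis by planned stratum.

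**2. Direction of movement**

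- Planned CABG alone, another major procedure added: randomised in the CABG-alone stratum, outside i-CABG.
- Planned combined surgery, only CABG done: randomised in the other stratum, inside i-CABG.
- CABG with a minor add-on: SAP 3.3 counts this as CABG alone for the planned category. SAP 3.2.4 excludes only an added major procedure but does not restate the minor add-on rule.

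**3. How many might move (assumed)**

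If 100 of 140 subjects are planned CABG alone and 3% to 10% change, then 100 × 0.03 = 3 to 100 × 0.10 = 10 subjects move, over both arms together.

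**4. Worst-case size under no device effect**

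Take the SAP Table 1 control rates for both arms: fatal bleeding 3%, UDPB ≥2 40.5%, components independent, CTD continuous. A subject with UDPB ≥2 beats a random subject of the other arm with probability

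0.97 × 0.03 + (0.97² + 0.03²) × 0.405 × 0.5 = 0.0291 + 0.9418 × 0.2025 = 0.220.

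If k such subjects are removed from a device arm of n and none from control, the device win fraction is f = (0.5n − 0.220k)/(n − k), and the win ratio is f/(1 − f).

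| n per arm | k | f | Win ratio |
|---|---|---|---|
| 65 | 3 | (32.5 − 0.66)/62 = 0.514 | 1.06 |
| 65 | 5 | (32.5 − 1.10)/60 = 0.523 | 1.10 |
| 50 | 3 | (25 − 0.66)/47 = 0.518 | 1.07 |
| 50 | 5 | (25 − 1.10)/45 = 0.531 | 1.13 |

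Simulation agrees to within about 0.01. It puts type I error at roughly 6% to 7% for k = 3 at 50 per arm, and 8% to 9% for k = 5. Equal losses (3 and 3, or 5 and 5) leave the win ratio at 1.00 by symmetry, and 3 against 2 gives about 1.02.

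**5. A less extreme model**

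Assumed inputs: no device effect, 60 planned CABG-alone subjects per arm, and 15% complex cases with UDPB ≥2 in 65% (against 40.5%) and 300 mL more drainage on a base of 800 (SD 500) mL. Only complex cases can be extended and so leave i-CABG.

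| Complex cases extended, device / control | Win ratio in performed i-CABG | Type I error |
|---|---|---|
| 50% / 50% | 0.99 to 1.00 | 5.0% to 5.2% |
| 70% / 30% | about 1.05 | 5.4% |
| 100% / 0% | 1.12 to 1.13 | 7.9% to 8.5% |

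Ranges are from two runs (3,000 and 8,000 trials). Analysed by planned stratum, type I error stayed close to 5% in all three cases (4.6% to 5.3% over both runs).

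**The case against.** The strongest reply is that a set formed after randomisation is still a fair comparison if membership does not depend on arm. Protocol 6.3 blinds the surgeon, the operating room staff and the anaesthesia team, who are the people who decide the operation. Protocol 6.1 attributes changes to factors that could not be foreseen, not to response to treatment. The documents offer no route by which drug removal would lead a blinded surgeon to add a valve or aortic procedure. This stands, and it means that bias is not shown.

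Four stronger readings are tempting, and the text does not support them.

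- *Membership is decided after device treatment starts.* This is true only of changes made during CPB. Others come before it, and protocol 6.1 allows for some to be updated in IxRS.
- *Heavy bleeders and long cases drop out.* SAP 3.2.4 excludes by type of procedure. A CABG-alone subject who bleeds, is re-explored or has a long CPB stays in the set.
- *Converted subjects also leave the PP set.* That needs the deviation to be graded major. SAP 4.3 gives the grading to blinded sponsor staff under a separate plan that is not among the documents, and protocol 6.1 says these subjects continue in the study.
- *The win ratios of 1.06 and 1.10 are an expected shift.* They need every lost subject to be a UDPB ≥2 bleeder and all of them to come from one arm.

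Two further points are fair. The i-CABG analyses are supplementary. And a set named for isolated CABG has a natural reading as the operation received, which is a defensible choice for safety.

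What remains is the mismatch itself: the SAP's i-CABG sets do not match the stratification factor or the protocol's subgroup, and no analysis bridges the two.

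**Conclusion.** The concern holds as a point about definition. The i-CABG mITT, PP and SA sets rest on the performed operation, which is settled after randomisation and possibly after device start, while the stratification and the protocol's subgroup rest on planned surgery. Subjects can cross in both directions, so the i-CABG comparison is not the randomised CABG-alone stratum.

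A reader might infer that the i-CABG result will be biased towards the device. The documents do not support that. Bias requires changes of operation to differ by arm, and with a blinded surgical team this is possible but not shown. If changes are equal by arm, the arms stay comparable and only the target population changes. The one-sided win ratios (1.06 to 1.13 under no effect) are upper illustrations. They rest on the SAP's component rates and on assumed numbers of converted subjects, because the documents give no conversion rate.

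The primary mITT analysis is unaffected. The change is still worth making before unblinding, because SAP 3.7 runs the whole hierarchy on i-CABG and the variable needed is already held.

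**What to change.** - **SAP 3.2.4:** define the i-CABG mITT and PP sets as the mITT or PP subjects whose final IxRS stratum before surgery was CABG alone. Minor add-ons are then handled by the rule already in SAP 3.3.
- **SAP 3.6:** use the same IxRS variable for the CABG against other procedures subgroup, so that it matches protocol 11.4.
- **Sensitivity analysis:** keep performed i-CABG as a labelled sensitivity analysis of effectiveness. SAP 3.2.5 may keep the performed definition for safety, provided it is labelled as such.
- **Table:** tabulate planned against performed surgery by arm, so that a reader can see whether changes were balanced.
- **Protocol 6.1:** state which IxRS entry is the final one. A change found in theatre comes after an assignment that must precede surgery, so the present wording leaves unclear how it could be updated.

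The cost is SAP wording, one sensitivity run and one table, with no new data. The downside is small: a few converted operations stay in a set named for isolated CABG, and the sensitivity analysis shows what they contribute.
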